1.0 INTRODUCTION

1.1 Overview

APP13007 is an ophthalmic nanosuspension that is prepared by dispersing nanomilled [REDACTED]
[REDACTED], a corticosteroid, with a mixture of excipients in a multi-dose preserved aqueous

1.2 Background

1.2.1 [REDACTED]

Corticosteroids regulate cellular signaling, immune function, inflammation and protein synthesis, and like other corticosteroids, CP has anti-inflammatory and vasoconstrictive properties. The mechanism of the anti-inflammatory activity of CP is unclear, but it is thought to act by inducing lipocortins, proteins that inhibit phospholipase A2, an enzyme that releases arachidonic acid from membrane phospholipids. By inhibiting phospholipase A2, lipocortins control the biosynthesis of potent mediators of inflammation such as prostaglandins and leukotrienes.

CP is an analog of prednisolone with a very high degree of activity at the glucocorticoid receptor and only slight degree of mineralocorticoid activity ([Clobex® 2018](#)). It is reported to be the most potent corticosteroid in terms of binding affinity to the glucocorticoid receptor and resulting pharmacological effects ([Olsen 1986](#)), ([Jacob 2006](#)). CP has been used in dermal applications including ointments, creams and shampoos, where its efficacy and safety has been well-established ([Clobex® 2018](#)); ([Temovate® 2000](#)); ([Olsen 1986](#)); ([Hengge 2006](#)); ([Feldman 2009](#)).

1.2.2 Pain and Inflammation Following Cataract Surgery

Despite modern advances in surgical technique, trauma that occurs during cataract removal and intraocular lens placement regularly leads to some degree of inflammation. The cellular damage on the surface of the cornea activates an inflammatory process that manifests initially as hyperemia, corneal edema, and increased anterior chamber cells and flare. More serious complications such as corneal edema, increases in intraocular pressure (IOP), cystoid macular edema (CME), and posterior capsule opacification may result if the inflammatory process is not managed appropriately ([Tennant 1978](#)) ([Apple 1992](#)). For this purpose, a post-cataract surgery regimen of anti-inflammatory agents (such as corticosteroids) is typically prescribed because it reverses inflammation, pain and discomfort and reduces the risk of further complications. When administered at the time of surgery and during the immediate postoperative period,

corticosteroids can reverse the clinical and non-clinical manifestations of inflammation ([Leopold 1985](#)) ([Aptel 2017](#)).

1.2.3 Rationale for Development of APP13007

Topical ocular administration of corticosteroids is a well-established therapy for the treatment of inflammation and pain after ocular surgery ([Aptel 2017](#)), and several marketed products are currently available that contain active ingredients such as dexamethasone, prednisolone, loteprednol etabonate and difluprednate.

[figure not shown]
CP has been used for over 30 years in the US, Europe and Japan to treat the inflammatory and pruritic manifestations of corticosteroid responsive dermatoses such as psoriasis, eczema and atopic dermatitis. CP has not been previously developed for ophthalmic use, presumably due to its lack of aqueous solubility. Nevertheless, given its increased potency, an aqueous ophthalmic formulation of CP has the potential to produce rapid clearance of anterior chamber cells (ACC), return of visual acuity and relief of pain after ocular surgery, surpassing the effectiveness of corticosteroids currently on the market.

APP13007 is an ophthalmic nanosuspension that is prepared by dispersing nanomilled CP with a mixture of excipients. The proprietary nanomilling technology allows CP to be formulated as an aqueous suspension. This suspension of CP nanoparticles in APP13007 is designed to promote efficient penetration of CP into the eye upon ocular surface instillation, thus delivering therapeutically relevant concentrations of CP to the target tissues within the eye.

[figure not shown]
1.3 Nonclinical Studies

Multiple nonclinical pharmacology, pharmacokinetics, and toxicology studies have been conducted with various formulations of APP13007, and these are summarized in the APP13007 Investigator Brochure.

1.3.1 Primary Pharmacology

1.3.2 Pharmacokinetics

1.3.3 Toxicology

Data from non-GLP and 14-day and 28-day Good Laboratory Practice (GLP) toxicity studies of APP13007 are summarized in the APP13007 Investigator Brochure.

[REDACTED] The toxicology studies suggest that potential systemic effects in human subjects with ocular instillations of APP13007 are those typical of corticosteroids in general and that have been seen with approved dermal CP products, such as Temovate® and Clobex® ([Temovate® 2000](#)); ([Clobex® 2018](#)).

The data from repeat dose toxicology studies did not identify any unacceptable risk for human subjects.

1.4 Human Studies

Two clinical studies have been completed with APP13007, and details of the subject populations, study dosing, conduct and results are summarized in the APP13007 Investigator Brochure.

[figure not shown]
[figure not shown]
1.4.1 CPN-201: A Phase 2 Safety and Preliminary Efficacy Study Post Cataract Surgery

This was a multi-center, randomized, double-masked, placebo-controlled, parallel-group Phase 2 study conducted in two parts (Parts A and B) to evaluate two APP13007 dose strengths and two dosing frequencies in subjects who had undergone routine cataract surgery and lens implantation. On Post-Operative Day 1 (POD1), subjects who met eligibility criteria were enrolled in the study and randomized to one of the study treatments instilled in the operated study eye: Treatment 1 or 2 in Part A (1:1 ratio); Treatment 3, 4, 5, or 6 in Part B (1:1:1:1 ratio). A total of 45 subjects were randomized in Part A and 87 subjects randomized in Part B.

[figure not shown]
- Treatment 1: 1 drop 0.05% APP13007 BID for 21 days
- Treatment 2: 1 drop 0.05% matching vehicle placebo BID for 21 days
- Treatment 3: 1 drop 0.05% APP13007 BID for 3 days followed by 1 drop 0.05% APP13007 QD for 11 days
- Treatment 4: 1 drop 0.05% matching vehicle placebo BID for 3 days followed by 1 drop 0.05% matching vehicle placebo QD for 11 days
- Treatment 5: 1 drop 0.1% APP13007 BID for 3 days followed by 1 drop 0.1% APP13007 QD for 11 days
- Treatment 6: 1 drop 0.1% matching vehicle placebo BID for 3 days followed by 1 drop 0.1% matching vehicle placebo QD for 11 days

1.4.1.1 Safety Results

The 0.05% APP13007 and 0.1% APP13007 dosing regimens were well-tolerated with a safety profile similar to the matching placebo vehicles.

1.4.1.2 Efficacy Results

1.4.1.3 Conclusion

The safety and efficacy results from study CPN-201 support the further clinical evaluation of 0.05% APP13007 BID for the treatment of inflammation and pain following ocular surgery.

1.4.2 CPN-102: A Phase 1 Pharmacokinetic Study in Healthy Subjects

CPN-102 was an open-label, sequential dosing, Phase 1 pharmacokinetic (PK) study to evaluate the systemic exposure of CP following ocular instillation of 0.05% APP13007 in healthy subjects.

1.4.2.1 Safety Results

The 0.05% APP13007 drops were well-tolerated. There were no AEs related to the study drug.

1.4.2.2 Pharmacokinetic Results

1.4.2.3 Conclusion

1.5 Risk/Benefit Assessment

1.5.1 Potential Risks

1.5.1.1 Potential Risks Anticipated Based on Results from the GLP Rabbit Toxicology Studies with APP13007

1.5.1.2 Potential Risks Anticipated Based on Results from the Human Studies with APP13007

As summarized in the APP13007 Investigator Brochure and in [Section 1.4.1.2](#) and [Section 1.4.2.2](#), 0.05% APP13007 BID for 21 days was well-tolerated. [REDACTED]

[REDACTED]
[REDACTED]
[REDACTED]
[REDACTED].

[REDACTED]
[REDACTED]
[REDACTED]
[REDACTED] the systemic tolerability profile after ocular instillation of 0.05% APP13007 BID for 14 days is expected to be considerably better than that for dermal CP products summarized below.

1.5.1.3 Potential Risks Associated with the Use of CP in the Treatment of Corticosteroid-Responsive Dermatoses

There is extensive experience with CP in the treatment of inflammatory and pruritic manifestations of corticosteroid-responsive dermatoses, where its safety and anti-inflammatory profile has been well defined (Olsen 1986); (Hengge 2006); (Feldman 2009). These risks are summarized in the APP13007 Investigator's Brochure.

Potential non-ocular risks include:

- Hypothalamic-Pituitary-Adrenal (HPA) Axis Suppression. Recovery of HPA axis function is generally prompt upon discontinuation of topical corticosteroids.
- Cushing's syndrome, hyperglycemia, and unmasking of latent diabetes mellitus. Use of more than one corticosteroid-containing product at the same time may increase the total systemic corticosteroid exposure.
- Skin: Allergic contact dermatitis may occur.
- Pregnancy and Nursing (Breast-feeding) Mothers:
 - Corticosteroids are teratogenic in laboratory animals when administered systemically at relatively low dosage levels (Pregnancy Category C). When administered subcutaneously, CP was a significant teratogen in both the rabbit and mouse. Females of child-bearing potential are eligible to participate in this study only if they have a negative urine pregnancy test on POD1 pre-randomization and they agree to use highly effective contraception from POD1 to POD22. Note: Pregnant and/or nursing (breast-feeding) mothers are excluded from participation in this study.
 - Systemically administered corticosteroids appear in human milk and could suppress growth, interfere with endogenous corticosteroid production, or cause other untoward effects. It is not known whether ocular administration of APP13007 could result in sufficient systemic absorption of CP to produce detectable concentrations in human milk.

Potential ocular risks are summarized below.

1.5.1.4 Potential Class-Related Ocular Risks Associated with Corticosteroid Therapies for the Treatment of Ocular Inflammation and Pain after Ocular Surgery

[figure not shown]
The active ingredient in APP13007, ■■■ is a potent corticosteroid so it has the following anticipated ocular risks associated with the corticosteroid class:

- Intraocular pressure (IOP) increase – prolonged use may result in glaucoma with damage to the optic nerve, defects in visual acuity and field of vision.
- Cataracts – Prolonged use ■■■ may result in posterior subcapsular cataract formation in the non-operated eye.

- Delayed healing – Use [REDACTED] after cataract surgery may delay healing and increase the incidence of bleb formation. In those diseases causing thinning of the cornea or sclera, perforations have been known to occur with the use of topical corticosteroids.
- Risk of Infection
 - Bacterial infections – Prolonged use [REDACTED] may suppress the host immune response and thus increase the hazard of secondary ocular infections. In acute purulent conditions, corticosteroids may mask infection or enhance existing infection.
 - Viral infections – Use of ocular corticosteroids may prolong the course and may exacerbate the severity of many viral infections of the eye (including herpes simplex).
 - Fungal Infections – Fungal infections of the cornea are particularly prone to develop coincidentally with long-term local corticosteroid application. Fungus invasion must be considered in any persistent corneal ulceration while a subject is participating in this clinical trial.

In clinical studies evaluating the use of corticosteroids after ocular surgery, ocular adverse reactions that occurred in 5% to 15% of subjects included corneal edema, ciliary and conjunctival hyperemia, eye pain, photophobia, posterior capsule opacification, anterior chamber cells, anterior chamber flare, conjunctival edema, and blepharitis. Other ocular adverse reactions occurring in 1% to 5% of subjects included reduced visual acuity, punctate keratitis, eye inflammation, and iritis. Ocular adverse reactions occurring in less than 1% of subjects included application site discomfort or irritation, corneal pigmentation and striae, episcleritis, eye pruritus, eyelid irritation and crusting, foreign body sensation, increased lacrimation, macular edema, sclera hyperemia, and uveitis. Most of these reactions may have been the consequence of the surgical procedure.

1.5.1.5 Potential Risks Associated with the APP13007 Formulation

1.5.2 Risk Mitigation Plan

Given the potential risks noted above, a risk mitigation plan will be used to mitigate risks for subjects enrolled into the study. The Risk Mitigation Plan is shown in [Table 2](#).

1.5.3 Contraindications

APP13007, as with other corticosteroids, is contraindicated in the presence of active viral diseases of the cornea and conjunctiva including epithelial herpes simplex keratitis (dendritic keratitis), vaccinia, and varicella, and also in subjects with mycobacterial infection of the eye and fungal diseases of ocular structures.

APP13007 must not be administered (i) to women of child-bearing potential without a negative urine pregnancy test on POD1 prior to randomization and agreement to use highly effective contraception or abstain from sexual activity from POD1 to POD22 or (ii) to pregnant or nursing (breast-feeding) woman.

1.5.4 Potential Benefits

Topical ocular administration of corticosteroids is a well-established therapy for the treatment of inflammation and pain after ocular surgery, with multiple marketed products currently available that utilize corticosteroids as the active ingredient such as dexamethasone (Maxidex®), prednisolone (PredForte®), loteprednol etabonate (Lotemax®, Inveltys®, Lotemax SM®), and difluprednate (Durezol®). In all clinical trials, corticosteroid therapies were dosed at a frequency of twice daily or more frequently.

As summarized in the APP13007 Investigator's Brochure, in Study CPN-201 a greater proportion of subjects treated with APP13007 0.05% BID had complete clearing of anterior chamber cells and complete resolution of ocular pain compared to placebo-treated subjects. Thus, it is likely that subjects randomized to active APP13007 will experience a clinically-meaningful reduction in inflammation and pain following cataract surgery.

It is known from large clinical trials of products for the treatment of inflammation and pain after ocular surgery that a proportion of subjects randomized to placebo improve in the days following surgery (Lotemax® Product Insert 2018; Durezol® Product Insert 2017). Thus, there may be a marginal benefit observed in some of the subjects enrolled into the study who are randomized to the matching vehicle placebo.

1.5.5 Assessment of Potential Risks and Benefits

This is a placebo-controlled study in which subjects will be randomized 1:1 to APP13007 or matching vehicle placebo. Subjects randomized to active APP13007 may benefit from the treatment by reduction in inflammation and pain, while the risks associated with active APP13007 treatment are likely to be low and manageable. This assessment is supported by the results of the nonclinical (See [Section 1.3](#)) and clinical studies (See [Section 1.4](#)) that are summarized in detail in the APP13007 Investigator's Brochure.

Subjects randomized to placebo are not expected to benefit from the study treatment, but a proportion of subjects receiving placebo may show improvement of inflammation in the days following surgery. Furthermore, the risks to subjects randomized to placebo in this study are mitigated as much as possible. Specifically, the protocol contains instructions for careful monitoring of safety and efficacy endpoints during the trial to identify subjects who show minimal improvement or worsening of the clinical conditions so that appropriate mitigation steps can be taken, including, but not limited to, withdrawal from study treatment and commencement of appropriate rescue medication.

Overall, the risk:benefit analysis supports the evaluation of 0.05% APP13007 and matching vehicle placebo administered BID for 14 days after cataract surgery.

Table 2: Risk Mitigation Plan

Potential Risk	Management	Comments
Risk Associated with Lack of Efficacy		
Minimal reduction or worsening of inflammation and pain endpoints or other factors suggesting lack of efficacy	Inflammation and pain endpoints will be monitored during the study. Guidance criteria and procedures for the rescue of subjects are provided in Section 9.4 of this protocol.	Minimal reduction or worsening of inflammation and pain endpoints or other factors suggesting lack of efficacy
Risk Associated with Unexpected Safety Events		
Unexpected safety events	Safety endpoints will be monitored during the trial. The Investigator will discuss unexpected safety events with the Study Medical Monitor who will then discuss unexpected safety events with the Sponsor to determine whether study drug should be stopped and rescue procedures commenced.	The toxicology studies with APP13007 indicate that there is a low risk of ocular toxicity. The risks of systemic exposure to CP following dermal application are well characterized. [REDACTED] [REDACTED] [REDACTED] [REDACTED] Nevertheless, the Investigator should be alert to the possibility

Potential Risk	Management	Comments
		that unexpected safety events may occur. The list of expected safety events is including in Section 1.5.5 and in the APP13007 Investigator's Brochure.
Risks Associated with the Corticosteroid Class		
Intraocular pressure (IOP) increase	
IOP will be monitored during the study. The protocol excludes subjects who may be at increased risk of steroid-induced IOP increase, e.g. subjects with a history of raised IOP/glaucoma and subjects with IOP >30 mmHg at the POD1 pre-randomization assessment.
 
Section 9.5 includes stopping criteria for study drug due to IOP increase and criteria for initiation of IOP-lowering medication.
 
After Randomization, the management of IOP > 30 mmHg or IOP ≥ 21 mmHg AND an IOP increase > 10 mmHg from pre-dose baseline is described in Section 9.5.2.
	
There was no clinically-meaningful APP13007-related elevation of IOP in the toxicology studies and in Study CPN-201.
 
Prolonged use of CP may result in glaucoma with damage to the optic nerve, defects in visual acuity and fields of vision.
 
An IOP ≥ 30 mmHg after randomization should be reported as an AE.

Cataracts	
The lens structure and posterior capsular opacification (POC) in the study eye will be monitored at each clinic visit throughout the study. The lens in the non-operated eye will be evaluated at Screening, Visit 6 (POD22) and Early Termination/Withdrawal visits.
	       
Delayed Healing	
Subjects with thinning of the cornea or sclera are excluded because of the greater risk of perforations with the use of topical steroids.
 
Protocol includes stopping criteria for study drug if the Investigator, in consultation with the Study Medical Monitor, is concerned about delayed healing.
	
Use of APP13007 may delay healing after cataract surgery and increase the incidence of bleb formation. There were no reports of delayed healing after cataract surgery in Study CPN-201.

Potential Risk	Management	Comments
Risk of Infection	
Subjects with on-going ocular bacterial, viral or fungal infections are excluded from the study.
 
Ocular infections occurring during the study should be assessed and treated appropriately.
 
The Investigator should discuss with the Study Medical Monitor whether to stop study drug if ocular infection occurs.
	
Use of APP13007 may suppress the host immune response and increase the hazard of ocular infections. This risk is likely to be low based on data from studies of other steroids products approved for the treatment of inflammation and pain after ocular surgery.

Hypothalamic-Pituitary-Adrenal Axis (HPA) Suppression	
Monitor for symptoms and signs of reduced adrenal function (including fatigue, muscle weakness, loss of appetite and weight, abdominal pain, nausea and diarrhea, low blood pressure, depression and irritability, salt craving and hypoglycemia).
 
The Investigator should discuss with the Study Medical Monitor who will then discuss with the Sponsor whether to stop study drug.
	
While systemic absorption of topical corticosteroids can produce reversible HPA axis suppression with the potential for glucocorticoid insufficiency after withdrawal from treatment, this risk is likely to be very low
 
[REDACTED]
 
[REDACTED]
 
[REDACTED]
 
[REDACTED]
 
[REDACTED]
 
Nevertheless, Investigators should be aware that the symptoms and signs of reduced adrenal function can be nonspecific and they should remain alert to the possibility that this may occur.

Effects related to excessive corticosteroid pharmacology	
Monitor for symptoms and signs of excess corticosteroid pharmacology such as Cushing's syndrome, hyperglycemia, and unmasking of latent diabetes mellitus.
 
The Investigator should discuss with the Study Medical Monitor who will then discuss with the Sponsor whether to stop study drug.
	
These effects have been reported after dermal use of CP and result from systemic absorption of topical CP.
 
The risk is likely to be very small
 
[REDACTED]
 
[REDACTED]
 
[REDACTED]

Pregnancy Category C/Fetal effects	
Women of child-bearing potential are excluded from the study if they have a positive urine pregnancy test on POD1 pre-randomization and/or do not agree to use highly effective contraception or abstain from sexual activity.
 
Pregnant and/or nursing (breast-feeding) mothers are excluded from the study.
	
Corticosteroids are known teratogens in laboratory animals when administered systemically at relatively low dosage levels.
 
[REDACTED]
 
[REDACTED]
 
[REDACTED]

Potential Risk	Management	Comments
Skin Irritation	
If irritation develops appropriate therapy should be instituted.
 
The Investigator should notify the Study Medical Monitor in advance if study drug is going to be stopped.
	
Allergic contact dermatitis may occur with CP.
 
Other skin reactions have been described with topical dermal products (See APP13007 Investigator's Brochure).

Other Potential Risks		
Hypersensitivity Reactions	
Subjects are excluded from the study if they have a history of hypersensitivity to CP, corticosteroids, [REDACTED] [REDACTED] [REDACTED] [REDACTED]
 
If hypersensitivity reaction occurs, the Investigator should discuss with the Study Medical Monitor who will then discuss with the Sponsor Medical Monitor whether to stop study drug.
	
Adverse reactions reported in clinical studies evaluating the use of corticosteroids after ocular surgery.	Most of these adverse reactions may have been the consequence of the surgical procedure and should be managed according to standard-of-care procedures.	Ocular adverse reactions reported in completed clinical studies of APP13007 are summarized in Section 1.5.1 .

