Collect and Check Diary Cards for Accuracy and Compliance				X	X		X	
AEs ⁷ and Concomitant Medications ¹¹	X	X ¹²	X	X	X	X ¹³	X	X

¹ Ophthalmic assessments will be performed in the study eye only at Visits 2-5; and performed on both eyes at Visit 1 (Screening) and at Visit 6 (POD22) or at subject Early Termination/Withdrawal.

² Surgery must occur between one to 28 days after Screening, preferably in the morning. If, due to unexpected events, surgery is postponed and would occur > 28 days past the Screening visit, contact the Study Medical Monitor to determine which, if any, of the screening procedures should be repeated. Subjects will be determined to be a suitable candidate for surgery during a pre-surgery medical assessment, where the routine medication list prescribed by the cataract surgeon should be reviewed to rule out prohibited medications (Section 5.4.2).

³ Visit 2 (POD1) should be scheduled between 18 to 34 hours following conclusion of surgery on Day 0. All assessments done on POD1 are done prior to Randomization to ensure eligibility. Note: Women-of-childbearing-potential are eligible for enrollment if they have a negative urine pregnancy test on POD1 prior to Randomization and they agree to abstinence from sexual activity or use of highly effective method of contraception.

⁴ Visit 5 (POD15) occurs on the day after the subject completes the study drug administration for 14 days. Women-of-childbearing-potential should have a urine pregnancy test.

⁵ Visit 6 (POD22) is the last visit for subjects who complete the study. Subjects who are withdrawn early should have the Visit 6 assessments and a urine pregnancy test performed before they are released from the study.

⁶ Includes assessments of ocular pain and irritation. See Section 8.0 of protocol for information on how to record AEs and how to determine attributability (relatedness) of AE to study procedures (including cataract surgery) or study drug.

⁷ Ocular inflammation assessment using ACC count, anterior chamber flare grade, bulbar conjunctival injection, sclera - ciliary flush and corneal edema.

⁸ IOP should (but not required) be assessed at each visit within ± 2 h of the IOP assessment time at Visit 1.

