4.2.1 Additional Inclusion Criteria on Postoperative Day (POD) 1/Day of Randomization (Visit 2)

- 8. Have undergone unilateral cataract extraction via phacoemulsification and posterior chamber intraocular lens implantation in the study eye without any additional procedures or complications that would, in the opinion of the Investigator, interfere with study procedures or confound study objectives
- 9. No significant ocular pathology affecting visual acuity that is identified after posterior chamber intraocular lens implantation in the study eye.
- 10. Have ≥ 10 cells in the anterior chamber (excluding red blood and pigment cells)
- 11. Have an IOP ≤ 30 mmHg. Note: If the IOP is elevated post-surgery, the investigator may use non-prostaglandin based IOP-lowering medication(s) at their discretion on the day of surgery (Day 0) only. The IOP will be measured and recorded on POD1 to determine eligibility for Randomization.

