4.3 Exclusion Criteria

Participants will be excluded if they meet any of the following criteria:

- 1. Have a known sensitivity or allergy to clobetasol propionate, corticosteroids, or any of the study medication's components including benzalkonium chloride and soybean lecithin or any routine medication required during cataract surgery or for the conduct of study procedures.
- 2. Have an ACC count > 0 or any evidence of intraocular inflammation (e.g., flare) in either eye at the Screening visit.
- 3. Have a Grade > 0 on the Ocular Pain Assessment in either eye at the Screening visit.
- 4. Have an immunosuppressive or autoimmune disease that in the opinion of the Investigator could affect intraocular inflammation or the normal healing process of the eye.
- 5. Have active or chronic/recurrent ocular or systemic disease that is uncontrolled and could affect wound healing and/or resolution of inflammation after cataract surgery.
- 6. Suspected or known malignancy or be currently receiving antineoplastic therapy.
Note: subjects with basal cell carcinoma will not be excluded unless the Investigator believes that the condition has the potential to interfere with study procedures or analysis of results.

7. Are using certain medications, namely:

- i. Subjects receiving treatment for macular degeneration (in either eye) with Eylea® (aflibercept), Avastin® (bevacizumab), Lucentis® (ranibizumab) Beovu® (brolucizumab-dbll) or Visudyne® (verteporfin) are excluded.
- ii. PROKERA (preserved amniotic membrane) is excluded from 1 year prior to the Screening visit to the end of the study.
- iii. Anti-inflammatory agents, analgesics (including opioids, narcotics, nonsteroidal anti-inflammatory drugs (NSAIDs), aspirin, acetaminophen and other pain medications) or immune-modulating agents systemically or in either eye from the beginning of the 'Washout' period in the List of Prohibited Medications ([Section 5.4.2](#)) until after the POD15 assessments, but preferably until after the POD22 assessments. *Note:*
(i) acetaminophen is permitted on the day of surgery; (ii) immunizations/vaccinations are permitted before and during the study.
- iv. Use of any of the prohibited medications listed [Section 5.4.2](#) within a time period prior to surgery that is less than the minimum 'washout' period noted in [Table 4](#).

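### The risk plan says subjects with corneal or scleral thinning are excluded, but none of the 39 numbered eligibility criteria names thinning

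*Protocol*

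**What the plan says.** Protocol Section 1.5.1.4, on risks of the corticosteroid class, names the hazard under delayed healing: "In those diseases causing thinning of the cornea or sclera, perforations have been known to occur with the use of topical corticosteroids". Table 2 in Section 1.5.5 gives the mitigation as settled fact: "Subjects with thinning of the cornea or sclera are excluded because of the greater risk of perforations with the use of topical steroids". The same row adds that the protocol has stopping criteria for use when the investigator is worried about delayed healing.

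Eligibility is set out in Sections 4.2 (inclusion 1 to 7), 4.2.1 (inclusion 8 to 11) and 4.3 (exclusion 1 to 28), and repeated in the synopsis. Section 6.2.3 tells sites to check Sections 4.2 and 4.3 on postoperative day 1 and to randomise a subject who meets all criteria. The contraindications in Section 1.5.3 concern infection ("APP13007, as with other corticosteroids, is contraindicated in the presence of active viral diseases of the cornea and conjunctiva", then mycobacterial and fungal disease), pregnancy and breast-feeding. They do not mention thinning.

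**The concern.** Two current parts of one protocol disagree about who may enter. Table 2 describes a categorical exclusion; the lists that decide randomisation do not contain it. Redaction does not explain the gap, because the numbered criteria are legible. Nor does the amendment log, because both texts are in force.

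What is at stake is subject safety. The sponsor identifies perforation as a known event with topical steroids in these eyes, and the study drug is a potent corticosteroid given for 14 days to an eye that has just been operated on. The row's other safeguard, stopping study drug, acts only after exposure. Section 9.1.1 does not list delayed healing among its stopping reasons; it is reached only through the general provision on deleterious effects in Section 9.1.1.3, which is discretionary.

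**Working it through.** No formula applies. The check is a comparison of texts with counts.

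**1. Criteria that name thinning.** Inclusion: 0 of 11. Exclusion: 0 of 28. Total: 0 of 11 + 28 = 39, in the body and again in the synopsis. In the protocol and SAP the word occurs only in Section 1.5.1.4 and Table 2.

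**2. Criteria that may catch a cause of thinning.** The documents do not list the diseases that thin the cornea or sclera, so this mapping is an assumption, made generously.

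| Exclusion | Subject | Limit in its own wording |
|---|---|---|
| 4 | "Have an immunosuppressive or autoimmune disease that in the opinion of the Investigator could affect intraocular inflammation" (or healing of the eye) | Investigator opinion |
| 5 | "Have active or chronic/recurrent ocular or systemic disease that is uncontrolled and could affect wound healing and/or resolution of inflammation after cataract surgery" | Disease must be uncontrolled |
| 10 | Past herpes keratitis | None counted |
| 11 | Corneal abrasions or ulcers | Must be active |
| 12 | Inflammatory eye disease, including scleritis, active or past | None counted |
| 13 | Ocular infections | None counted |
| 14 | Corneal dystrophies, dysthyroid eye disease | None counted |
| 17 | Corneal or retinal surgery | Within 6 months of Screening, or planned during the study |
| 19 | Trauma with scarring or deformity | Investigator opinion |

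That is nine exclusion criteria, of which at least five (4, 5, 11, 17, 19) are limited. Two inclusion criteria arguably help. Inclusion 8 requires surgery "without any additional procedures or complications that would, in the opinion of the Investigator, interfere with study procedures" or confound the objectives. Inclusion 9 reads "No significant ocular pathology affecting visual acuity that is identified after posterior chamber intraocular lens implantation in the study eye", so it concerns only pathology that affects acuity.

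**3. The catch-all.** Exclusion 27 covers any other condition the investigator decides should exclude the subject. It permits exclusion for thinning; Table 2 says the exclusion applies.

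**4. Can a subject pass?** As an illustration from the wording alone, suppose corneal surgery more than 6 months before Screening left a thin, stable cornea with no effect on acuity. Exclusion 17 does not apply, and if none of the other listed conditions is present only exclusion 27 remains. The site could randomise this subject without a deviation from Sections 4.2 and 4.3.

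**5. Other exclusions stated in Table 2.** Five rows state an exclusion. Four have a criterion on the subject of the stated exclusion: intraocular pressure (exclusion 9, inclusion 11), infection (exclusion 13), pregnancy (inclusion 3 and 4) and hypersensitivity (exclusion 1). The match is by topic and not exact: exclusion 13 covers only the study eye, exclusion 9 needs repeated documented elevation, and the hypersensitivity row is partly redacted. The exclusion for thinning is the one without a counterpart.

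**6. Slit-lamp items.** Table 1, footnote 7 lists five: "Ocular inflammation assessment using ACC count, anterior chamber flare grade, bulbar conjunctival injection, sclera - ciliary flush and corneal edema". None is thinning.

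**The case against.** The strongest reply is that this is a gap in cross-referencing and not in protection. Table 2 is part of the protocol, and an investigator who sees thinning has a written statement there and exclusion 27 with which to act on it. A pre-surgery medical assessment (Section 3.2.1) gives a further clinical check. Exclusions 4, 5 and 19 refer expressly to healing, which is the title of the Table 2 row, so the four-of-five contrast reads this row more narrowly than the others. Section 1.5.1.4 speaks of diseases that cause thinning, whereas the illustration uses old surgery. Footnote 7 lists inflammation items only; abrasions and dystrophies are not on it either, yet they are enforceable criteria. Finally, exclusion 17 admits older corneal surgery, so a new criterion would remove some subjects now allowed.

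Several of these points stand. The slit-lamp count proves little, the four-of-five contrast depends on how the row's topic is read, and the illustration is only an example of wording. The contradiction needs none of them. Exclusion 27 is discretionary, the pre-surgery assessment does not name thinning and is optional in Section 6.2.1, and Section 6.2.3 sends sites to Sections 4.2 and 4.3, not to Table 2. The illustrated eye also falls under Table 2 as written, which speaks of thinning without regard to cause. Any narrowing of the population is therefore what Table 2 already prescribes.

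**Conclusion.** The concern holds. The protocol states an exclusion for corneal or scleral thinning that 0 of its 39 numbered criteria names, and the criteria that do reach some causes leave a route by which such a subject can be randomised in full compliance. The gap is probably small: nine exclusion criteria catch some causes, and an attentive investigator may use exclusion 27. It cannot be quantified, because the documents give no prevalence. Alpha, power, sample size and the primary analysis are unaffected. The finding that no criterion names thinning rests on the text alone; the estimate of how much the other criteria cover rests on the assumed mapping in step 2. Correction should be made, since this is a stated safety measure that the operative criteria do not carry out.

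**What to change.** Add an exclusion criterion to Section 4.3 and the synopsis: *thinning of the cornea or sclera in the study eye, as judged by the Investigator on slit-lamp examination at Screening*. Limiting it to the study eye fits the dosing. If the sponsor intended only the existing criteria, reword the Table 2 row to cite them by number. The added criterion is preferable because the protocol names perforation as a known risk.

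The cost is one line in an amendment and possibly a few more screen failures, including some subjects with older corneal surgery whom exclusion 17 now admits. No new procedure is needed: Table 1 and Section 6.2.1 already require slit-lamp examination of both eyes at Screening. The judgement stays with the investigator and no thickness threshold is set, but a finding of thinning would then require exclusion.
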